9. INTERIM ANALYSIS

No interim analysis is planned for this study.

10.DATA CONVENTIONS FOR ANALYSIS

10.1General Statistical Principles

All statistical processing will be performed using SAS® unless otherwise stated. Any statistical tests will be two-tailed at significance level of 0.05 unless otherwise specified.

All observed and derived variables (e.g., change from baseline, percentage change from baseline, and response status) used in the summaries of analyses will be presented in by-subject listings. Unless otherwise noted, the data will be sorted first by treatment assignment, then by subject number and then by date within subject number.

Efficacy and safety results will be summarized descriptively. Categorical parameters will be summarized by the number and percentage of subjects in each category. Denominators for percentages will be appropriate to the purpose of the analysis. Percentages will typically be presented to one decimal (Note: 0% and 100% will be in integer format). Continuous parameters will be summarized as number of subjects, mean, standard deviation (SD), median, minimum, and maximum.

10.2Study Day

Day 1 is defined as the date of first study drug administration. Study day is calculated relative to the date of Day 1. For subjects who did not have a recorded date of first study drug administration, study day will not be calculated.

10.3Baseline and Change from Baseline

Baseline is defined as the last non-missing assessment prior to the first administration of study drug. Change from baseline is defined as post-baseline value minus baseline value unless otherwise specified. Percent change from baseline is (Change from baseline / Baseline) * 100%.

10.4Analysis Visit Window

Results will be summarized according to the visit as recorded in the eCRF. No visit windows will be applied.

10.5Multiple Comparisons

Not applicable. There will be no formal hypothesis testing.

11.STATISTICAL EVALUATION

11.1Subject Disposition

The number and percentage of subjects screened, enrolled, included in key analysis populations, completing the study, and withdrawing from the study (together with the reasons for withdrawal) will be summarized using frequencies and percentages, overall and by cohort (treatment-duration-increment, expansion).

A by-subject listing will show all subjects enrolled and their disposition.

The number of days in the study (date of study completion / discontinuation minus date of Day 1 plus 1) will be summarized descriptively, overall and by cohort (treatment-duration-increment, expansion).

11.2Protocol Deviation

Protocol deviations will be logged throughout the study and classified as minor or major. Major protocol deviations will be summarized for all enrolled patients.

All protocol deviations will also be listed by subject.

11.3Demographic and Baseline Characteristics

Demographics and baseline characteristics will be summarized separately in mBCC and locally advanced BCC groups as well as overall for the Safety and Efficacy populations. The following demographic and baseline variables will be included:

- Age (years)
- Gender
- Race
- Ethnicity
- Weight (kg)
- Height (cm)
- BMI (kg/m^2)
- ECOG performance status

11.4Disease History

For the summary of BCC history, the following will be summarized separately in mBCC and locally advanced BCC groups and listed:

- Time since diagnosis (calculated as year of informed consent year of initial diagnosis)
- BCC variant (nodular, superficial, infiltrative, basosquamous, other)
- Gorlin's syndrome (Y, N)

11.5Prior Therapy

Prior BCC therapy will be listed in three separate listings: (i) radiotherapy, (ii) systemic therapy, and (iii) anti-cancer surgery.

The summary of prior **radiotherapy** will include a summary of radiotherapy locations, including all locations recorded for each subject.

The summary of prior **systemic therapy** will include the total number of systemic therapies, the therapy type(s), and the time between end of last treatment to start of study treatment, and the best response after each treatment up to and including the last recorded.

The summary of prior **anti-cancer surgery** will include the time between the last surgery to start of study treatment and reason for surgery.

All summaries will be provided separately in mBCC and locally advanced BCC patients as well as overall.

11.6Study Medication Exposure

The following parameters of study drug exposure will be summarized for the RDI population:

- Cumulative dose (g), calculated as total number of capsules taken per subject diary* 0.2g, for each cycle and overall.
- Dose intensity (g/day, calculated as [cumulative dose (g) / duration of dosing (days)]), defined for each cycle
- Planned dose intensity (g/day, 1000mg BID=2g/day), defined for each cycle
- Relative dose intensity (% of planned, calculated as [dose intensity / planned dose intensity] *100), defined for each cycle

Cumulative dose will also be summarized for the Safety population.

11.7Prior and Concomitant Medications

Prior (within the previous 7 days and with stop dates prior to first dose of study drug) and concomitant (ongoing or with stop dates on or after first dose of study drug) medications will be presented for the safety population in a by-subject listing. If the medication is ongoing or the stop year is missing, the medication will be considered as received for the entire duration of the study. Medications will be coded using WHO-DD terminology.

For the determination of prior vs concomitant medications, the following rules regarding the stop date will be applied:

- If only year was recorded, and it is before Baseline, it is a prior medication; if year is same or after Baseline, it is assumed to be a concomitant medication.
- If day is missing, but month and year are before Baseline, it is a prior medication; if month and year are the same as Baseline, it is assumed to be a concomitant medication; if month and year are after Baseline, it is a concomitant medication.
- If start date is after Baseline, it is a concomitant medication regardless.

Concomitant medications will be summarized by WHO-DD Anatomical-Therapeutic-Chemical (ATC) classification level 4 or highest level available and preferred term (PT).

Use of dispensed anti-emetics and use of dispensed loperamide will be listed in separate listings.

11.8Medical History and Concurrent Procedures

Medical history (including previous and ongoing medical conditions) will be coded using MedDRA (version 23.0) and summarized by System Organ Class (SOC) and preferred term (PT).

11.9Efficacy Endpoints

11.9.1 Primary Efficacy Endpoints

The efficacy endpoints include the following:

• **Best Overall Response**: Assessed separately for patients with mBCC and with locally advanced BCC as a function of radiographic, photographic, and pathologic review (Appendices B, C, G and H of the protocol) as described below.

For patients with mBCC: Overall Response will be assessed using the Response Evaluation Criteria in Solid Tumors (RECIST).

For patients with locally advanced BCC: Overall response will be assessed using a composite response endpoint that incorporates externally visible tumor dimension and tumor ulceration, as well as RECIST for lesions with a RECIST-measurable component.

Patients will be categorized as Complete Response (CR), Partial Response (PR), Stable Disease (SD), Progressive Disease (PD), and Not Evaluable (NE) in Overall Response at each assessment.

• **Objective Response**: Defined as a Complete Response (CR) or Partial Response (PR) in Overall Response determined on two consecutive assessments ≥ 4 weeks apart.

In patients with locally advanced BCC achieving a CR or PR, tumor biopsies will be used in the final determination of CR. CR is defined as absence of residual BCC on biopsy; PR is defined as presence of residual BCC on biopsy.

• Analysis of the changes in *Gli1* expression will be conducted by the OncoCyte Corporation (formerly Insight Genetics) and a separate report will be prepared. Thus detailed analysis is not included in this SAP.

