10.1.2. Exclusion Criteria

Patients who meet the following criteria will be excluded from study entry:

- 1. Pregnant or nursing women. NOTE: Women of child-bearing potential and men must agree to use adequate contraception (hormonal or barrier method of birth control; or abstinence) prior to study entry and for the duration of study participation. Should a man father a child, or a woman become pregnant or suspect she is pregnant while participating in this study, he or she should inform the treating physician immediately.
- 2. Concurrent non-protocol-specified anti-tumor therapy (e.g., chemotherapy, other targeted therapy, radiation therapy, or photodynamic therapy)

- For patients with multiple cutaneous BCCs at baseline that are not designated by the investigator as target lesions, treatment of these non-target BCCs with surgery may be permitted but must be discussed with the Medical Monitor prior to any surgical procedure.

- For patients with locally advanced BCC whose target lesion(s) is/are inoperable at baseline but is/are later deemed potentially operable because of tumor response to CX-4945, surgery with curative intent may be permitted but must be discussed with the Medical Monitor prior to any surgical procedure.

- 3. History of other malignancies within 3 years of Day 1, except for tumors with a negligible risk for metastasis or death, such as adequately treated squamous-cell carcinoma of the skin, ductal carcinoma in situ of the breast, or carcinoma in situ of the cervix.
- 4. Active or uncontrolled infections or with serious illnesses or medical conditions which would not permit the patient to be managed according to the protocol.
- 5. History of other disease, metabolic dysfunction, physical examination finding, or clinical laboratory finding giving reasonable suspicion of a

disease or condition that contraindicates use of an investigational drug or that might affect interpretation of the results of the study or renders the patient at high risk from treatment complications.

- 6. Difficulty with swallowing oral medications.
- 7. Chronic diarrhea (excess of 2-3 stools/day above normal frequency).

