11.5. CONCOMITANT AND EXCLUDED THERAPIES

Concomitant Therapy

Concomitant therapy includes any prescription medications or over-the-counter preparations used by a patient between the 7 days preceding the screening evaluation and the end of study visit. All concomitant medications should be reported to the investigator and recorded on the appropriate electronic Case Report Form (eCRF).

Excluded Therapy

Although no specific concomitant medications are prohibited during this study, concomitant medications should be used with care, and the risk-benefit profile of each agent should be taken into consideration. Concomitant medications that may

potentially interact with CX-4945 are listed in Appendix F. This is not necessarily a complete list; other medications may also interact with CX-4945.

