• Sample analysis (fresh frozen tissue or formalin fixed paraffin embedded): Tumor histology will be reviewed and Hh pathway target gene (*GLI1*) and reference gene expression profiling will also be performed on the tumor tissue sample obtained from patients with locally advanced BCC at baseline and at 8 weeks following CX-4945 treatment in order to evaluate the effect of CX-4945 treatment on the Hh signaling pathway.

h. Early Termination or End of Study Assessments

Patients who discontinue from the study will be asked to return to the clinic within 30 days of the last dose of CX-4945 for a follow-up visit. In patients with locally advanced BCC, biopsy of tumor at the time of progression for submittal for pathology review is strongly encouraged.

i. Follow-up Off Protocol Treatment

All patients will be seen at 4 weeks after completion of protocol therapy. Thereafter, continued follow-up is not required for patients who go off protocol treatment with progressive disease, except to document ongoing toxicities (until resolved to < grade 2) and late toxicities (including second malignancies). For patients who go off protocol treatment with CR, PR, or SD ongoing, follow-up will be required every 3 months until relapse (see Appendix A for investigations to be performed). Death report will be required on all patients unless advised by the Sponsor and due within 2 weeks of knowledge of death (see Section 16.3.1).

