^b If the investigator's assessment of progressive disease is equivocal, and in the investigator's opinion the patient is still deriving benefit from treatment, treatment with CX-4945 should be continued, and the patient should be re-evaluated at the next tumor assessment timepoint.

In patients with a clinical response, histologic analysis of biopsies will be used for final determination of CR (absence of residual BCC) versus PR (residual BCC present); see Appendix G.

In addition, if all previously inoperable target lesions are rendered operable with clear margins obtained at the time of surgery, this will be considered a PR. If the investigator deems a previously inoperable lesion to be potentially operable, the Medical Monitor should be consulted prior to any surgical procedure

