11.9.2 Other Efficacy Endpoints

- **Progression Free Survival (PFS):** Defined as the time from the date of the first dose of study drug until the date of progressive disease or death from any cause, whichever occurs first. PFS will be censored as follows:
 - Patients who had no event (i.e., they did not die or have PD) will be censored at the date of their last tumor assessment.
 - Patients with no baseline assessment will be censored at the date of the first dose.
 - Patients who started a new anti-cancer therapy prior to documented PD or death will be censored at the last tumor assessment prior to initiation of new anti-cancer therapy.
- **Duration of Response (DOR):** Defined as the time from the date of first documented response (CR or PR) until the date of progressive disease or death from any cause, whichever occurs first, after achieving response. DOR will be censored as follows:
 - Patients who had no event (i.e., they did not die or have PD) will be censored at the date of their last tumor assessment.
 - Patients who started a new anti-cancer therapy prior to documented PD or death will be censored at the last tumor assessment prior to initiation of new anti-cancer therapy.
- **Duration of Stable Disease (DSD):** Defined as the time from the date of first documented Stable Disease (SD) response until the date of progressive disease or death from any cause, whichever occurs first, after achieving SD response. DSD will be censored as follows:
 - Patients who had no event (i.e., they did not die or have PD) will be censored at the date of their last tumor assessment.
 - Patients who started a new anti-cancer therapy prior to documented PD or death will be censored at the last tumor assessment prior to initiation of new anti-cancer therapy.
- **Disease Control Rate (DCR):** Defined as the percentage of patients who have achieved CR, PR, or SD lasting at least 6 months.
- **Duration of Disease Control (DDC):** Defined as the time from the date of first documented response (CR or PR) or Stable Disease (SD) until the date of progressive disease or death from any cause, whichever occurs first, for patients with CR, PR or SD lasting at least 6 months. DDC will be censored as follows:
 - Patients who had no event (i.e., they did not die or have PD) will be censored at the date of their last tumor assessment.

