11.10 Efficacy Analyses

11.10.1Primary Efficacy Analyses

The primary endpoints will be assessed in the Efficacy population, overall and separately for patients with mBCC and patients with locally advanced BCC.

The objective response rate (ORR) will be calculated as the number of patients satisfying the OR criteria divided by the number of subjects in the Efficacy population. Patients without at least one post-baseline response assessment will be treated as non-responders. Further, patients who experience progressive disease but continue treatment under the protocol and experience partial or complete response in a subsequent tumor assessment, will be considered partial or complete responders. A continuity-corrected 95% confidence interval based on the normal approximation will accompany each ORR.

Complete response rates (CRR) will be summarized in parallel fashion to ORR.

11.10.20ther Efficacy Analyses

PFS will be analyzed using the Kaplan-Meier method in the Efficacy population, separately for patients with mBCC and patients with locally advanced BCC.

Summary statistics from the Kaplan-Meier distribution will be determined, including the median and estimates at 3, 6, 9, 12 months. These statistics will be provided as point estimates with 95% confidence intervals.

DOR summary will include at least median (in months), range and patients (n, %) with observed DOR for at least 6 months.

DSD summary will include at least median, range, min, max and patients (n, %) with observed SD for at least 6 months.

DCR summary will include at least median, range, min, max and patients (n, %) with observed DCR for at least 6 months.

Summary of patients with CR+PR+SD (regardless of duration) will include at least median, range, min, max and patients (n, %) with observed CR+PR+SD.

11.10.3Subgroup Analyses

Not applicable.

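### Objective response has no cut-off at new anti-cancer therapy, although PFS and DOR do, so a patient who stops CX-4945 without progression can be a responder on later treatment and have a negative duration of response

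*SAP*

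**What the plan says.** **Response.** SAP 11.9.1 gives objective response as "Defined as a Complete Response (CR) or Partial Response (PR) in Overall Response determined on two consecutive assessments" at least 4 weeks apart. SAP 11.10.1 divides the responders by the Efficacy population and treats CRR the same way. Neither section mentions new anti-cancer therapy. The only condition on treatment concerns responses after progression: "patients who experience progressive disease but continue treatment under the protocol and experience partial or complete response in a subsequent tumor assessment" count as responders. Protocol Appendix B (3.2.3) closes the best-overall-response window at progression or recurrence.

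**Durations.** In SAP 11.9.2, DOR is "Defined as the time from the date of first documented response (CR or PR) until the date of progressive disease" or death. For PFS, DOR, DSD, DDC and the duration of CR+PR+SD, the censoring rule reads "Patients who started a new anti-cancer therapy prior to documented PD or death will be censored at the last tumor assessment prior to initiation" of that therapy. The term new anti-cancer therapy is not defined.

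**Follow-up off treatment.** For patients who leave treatment with CR, PR or SD, Protocol 12.1(i) says that "follow-up will be required every 3 months until relapse". In the Appendix A flowchart, footnote s repeats this for tumour assessments. Footnote r, the 4-week confirmation scan, is attached to the same follow-up column. Starting another therapy does not end these assessments.

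**Surgery.** For locally advanced disease, Appendix C adds that "if all previously inoperable target lesions are rendered operable with clear margins obtained at the time of surgery, this will be considered a PR". Exclusion criterion 2 (Protocol 10.1.2) links such surgery to operability gained through response to CX-4945.

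**The concern.** By censoring five duration endpoints for it, the SAP accepts that some patients will start new therapy before progression. It sets no matching limit on the response endpoints that share the same assessments. A response reached on the next treatment can then be credited to CX-4945, and the response and duration rules contradict each other for that patient.

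The trial is single-arm and open-label with very small cohorts, and for ORR this error acts only upward. The sample-size section treats 2 responses in 10 as enough to suggest further study, so a single misattributed response matters.

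**Working it through.** **1. Which patients can be affected**

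- *Progression first:* largely closed. Appendix B ends best overall response at progression, SAP 11.10.1 credits a later response only if protocol treatment continued, and Protocol 12.1(i) requires no further follow-up after progression except for toxicities.
- *Stopped CX-4945 without progression, mainly with SD:* open. None of those limits applies, assessments continue every 3 months, and two of them 3 months apart satisfy the 4-week confirmation interval.

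**2. The duration this produces**

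DOR = censoring date - date of first response. On this route the last assessment before new therapy precedes that therapy, which precedes the response. DOR is therefore negative whatever the dates; only its size depends on them. All dates below are assumptions.

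| Last assessment before new therapy | New therapy | First PR | Confirmed | ORR | DOR |
|---|---|---|---|---|---|
| Day 113 (SD) | Day 140 | Day 204 | Day 295 | responder | 113 - 204 = -91 days |
| Week 16 (SD) | Week 18 | Week 28 | Week 32 | responder | (16 - 28) x 7 = -84 days |

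PFS for the same patients is censored at Day 113 and Week 16, before the response that ORR counts.

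**3. The plan's own figure**

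Protocol 15.6 and SAP 6 give an 80% interval of (5.5%, 45.0%) for 2/10. The exact (Clopper-Pearson) limits solve P(X >= 2 | p) = 0.10 and P(X <= 2 | p) = 0.10 with n = 10. They are 5.45% and 44.96%, so the figure is reproduced.

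**4. Effect of one misattributed response in a cohort of 10**

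- Rate: 1/10 = 10 percentage points.
- Without it, 2/10 becomes 1/10. The lower limit is 1 - 0.9^(1/10) = 1.0% and the upper limit 33.7%. The lower limit moves from above 5% to below it.
- At a true rate of 5%, P(X >= 2) = 1 - 0.95^10 - 10 x 0.05 x 0.95^9 = 8.6%. If one credited response is always spurious, one genuine response suffices: 1 - 0.95^10 = 40.1%.
- If each non-responder has an assumed chance q of a credited off-drug response, the apparent rate is p = 0.05 + 0.95q:

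| q (assumed) | p | P(X >= 2 of 10) |
|---|---|---|
| 2% | 6.9% | 14.8% |
| 5% | 9.75% | 25.4% |
| 10% | 14.5% | 43.7% |

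**5. Metastatic cohort**

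SAP 6 reports 2 expansion patients, so one response is 1/2 = 50 points. The Efficacy population also includes run-in patients (3 to 6 planned). With k of them metastatic, the effect is 1/(2 + k): 33 points for k = 1, 20 for k = 3, 12.5 for k = 6.

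**6. Surgical partial response**

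Appendix C grants the PR at resection, whereas SAP 11.9.1 requires two consecutive assessments. Neither document says how a resected lesion meets that requirement or on what date the PR falls. With SD to Week 24 and surgery at Week 26 (assumed), and the PR dated at surgery, DOR is (24 - 26) x 7 = -14 days if surgery counts as new anti-cancer therapy. If it does not, PFS and DOR run on after the tumour has been removed.

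**The case against.** **The route is narrow.** Treatment continues until progression, intolerable toxicity or withdrawal, and follow-up ends if consent is withdrawn. That leaves mainly patients who stop for toxicity without progression. This stands: a reader might infer that next-line therapy in general is credited to CX-4945, but the post-progression limits in step 1 do not support that.

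**Surgery is a deliberate rule.** A reader might also infer that surgical credit is a missing cut-off, or that Appendix C should demand prior shrinkage. It is an explicit, prospective definition. It requires all inoperable target lesions to become operable with clear margins, calls for consultation with the Medical Monitor, and is tied to response by exclusion criterion 2. Adding a shrinkage threshold would be a trade-off, and would redefine response after patients had been enrolled in an open-label trial. The gap is only in confirmation, dating and censoring.

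**Other inferences that fail.**
- The rate of CR+PR+SD regardless of duration is not inflated here: a patient who stopped with SD already counts in it.
- Protocol 11.5 ("Although no specific concomitant medications are prohibited during this study") sits awkwardly beside exclusion criterion 2 ("Concurrent non-protocol-specified anti-tumor therapy"). However, 11.5 concerns concomitant medication and interactions, while this gap arises after CX-4945 stops. The two texts merit reconciling, but they do not cause the problem.
- Response is not the only antitumour evidence. PFS, disease control and pathological absence of residual tumour are also planned.

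**The stakes are limited.** RP2D is the primary endpoint, efficacy is descriptive without formal testing, and by-subject listings would help to expose an affected patient. This stands and lowers the severity. It does not settle which ORR is reported, or what DOR to give a patient censored before responding.

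**Conclusion.** The point holds for patients who start other therapy without progression. Followed as written, the plan can count a response obtained on later treatment and assign that patient a negative DOR, and no SAP rule resolves the conflict.

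One such patient moves a cohort of 10 by 10 points and can carry the 80% lower limit from 1.0% to 5.5%, across the 5% no-interest rate. In metastatic disease the effect is at most 50 points, and less with any metastatic run-in patients. This rests on assumed dates and on a locally advanced denominator of 10, which run-in patients or incomplete enrolment would change. The threshold comparison uses the sample-size section's 80% interval, not the 95% interval planned for reporting ORR. The number of affected patients is unknown and may be zero.

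Severity is moderate. The SAP labels response a primary efficacy endpoint, but in the protocol it is a descriptive secondary outcome, and RP2D is unaffected.

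**What to change.** 1. **SAP 11.9.1 and 11.10.1:** derive best overall response, ORR, CRR and DCR only from assessments up to the last one before new anti-cancer therapy, the cut-off already used for PFS and DOR.
2. **SAP 11.9.2:** define new anti-cancer therapy, stating whether it includes radiotherapy to, and surgery on, target lesions.
3. **Surgical PR:** leave the Appendix C rule in place. In the SAP, reconcile it with the two-consecutive-assessment requirement, state how such a PR is dated and how PFS and DOR are then censored, and show ORR with and without surgical PRs.

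**Cost.** A few SAP sentences and one extra ORR line. ORR may be slightly lower. The sponsor should check that start dates of new therapy are collected in the 3-month follow-up: as extracted, the flowchart shows no concomitant-medication or cancer-procedure entry in that column, though the table may be broken. PFS and DOR censoring already needs those dates. The change belongs in the SAP itself, because SAP 12 gives any analysis change not specified there exploratory status.
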